#### **Abbreviations**

General Medical Services (GMS)

Intention to Treat (ITT)

Hospital Consumer Assessment of Healthcare Providers and Systems (HCHAPS)

Vanderbilt University Medical Center (VUMC)

Vanderbilt Institute for Clinical and Translational Research (VICTR)

Center for Clinical Quality and Implementation Sciences Research (CCQIR)

Post Hospital Discharge Follow-Up Phone Call Data Collection form (Phone Call Starform)

Research Derivative (RD)

Department of Quality, Safety and Risk Prevention (QSRP)

Application Program Interface (API) Electronic Health Record (EHR)

#### **Study Summary**

Study Start: February 13, 2017 (1 week run-in period) Accrual Start: February 20, 2017 (NCT03050918) Primary Outcome: Readmission within 30 days

[figure not shown]
Primary Analysis: Intention to Treat

- Study length/accrual period: ~7 months
- Follow up: 45 days
- Sample size: 3556 (1778 per arm)
- Baseline event rate = 13.5%
- Target detectable difference of 3.5% (13.5% controls, 10% intervention)
- Power 90% (chi square)

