#### STUDY TIMELINE: UPDATED

- 1. Adult Executive Quality Committee 3 month Update June 21, 2017
- a. Analysis: [name] (descriptive, no outcome data)
  - Table 1 Patient demographics
  - Overall VUMC readmission rate
  - Summary of phone call nurse patient interventions
- b. Presenters: [name], [name], [name]
- 2. Blinded Interim Analysis 50% patient enrollment ~July 2017
- a. Content ([name])
  - 2 week analysis window: Alpha 0.005, no stopping/futility rules
  - Patient demographics (by study arm, Table 1)
  - VUMC readmission rate by study arm and assessment of significant difference
  - Pre-specified subgroup analysis for readmission yes/no
  - Will not include the reachability index at this time.
  - Will only use death data from VUMC and available Patient Satisfaction data
  - See Appendix V for details
- b. Safety Review August 2017
  - Safety Committee Members: [name], [name], [name]
  - Review of Discharge Phone Call RN's daily reports to her supervisors for safety issues.
  - Interim Analysis Preparation and Presentation: [name]
- 3. Enrollment End 100% patient enrollment end: ~Sept 20, 2017
- a. Readmit f/u end: ~Nov 5, 2017
- b. Freeze database after Patient Satisfaction data (2mo lag) included: ~Nov 20, 2017
- c. Re-open database to add death + external hospital readmission data (6-8mo lag): ~May 20, 2018
- d. Death date source: VUMC EHR
- e. External hospital readmission data source: Vanderbilt Health Affiliated Network (VHAN)
- 4. Adult Executive Quality Committee Presentation Study End Early Findings Jan 2018
- a. Final analysis findings, except for death data
- b. 2 week analysis window: Alpha 0.048
- 5. Final Analysis June 2018
  - a. Content ([name] and [name])
    - 2 week analysis window: Alpha 0.048
    - Patient demographics (by study arm, Table 1)
    - VUMC readmission rate by study arm and assessment of significant difference
    - Pre-specified subgroup analysis for readmission yes/no
    - Identical to the Interim Analysis plan except all patient satisfaction, external hospital readmission, and mortality data will be included.

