#### Statistical Analysis

In our univariate analysis, differences among these patient characteristic groups will be assessed using the continuity corrected chi-square test or Mann-Whitney test for continuous outcomes and the Kruskal-Wallis test for categorical outcomes. In our multivariate analysis, we will examine the relationship between treatment assignment and our secondary endpoints using logistic regression. The study is not powered for a time-to-event analysis; however, we will explore time-to-readmission using the Cox proportional hazard model to understand the timing of when readmissions occur. In order to provide VUMC Leadership with preliminary efficacy data, we will perform an interim analysis at 50% enrollment ( $\sim$ 3.5 months) followed by the final analysis at study completion months ( $\sim$ 7 months). See **Appendix V** for details. We have pre-specified an  $\alpha$ -level of significance of 0.05 with penalties for a mid-study interim analysis per the O'Brian-Fleming alpha spending function allowing for an  $\alpha$ -significance level of 0.005 for the interim analysis and 0.048 for the final analysis.

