### **Power Calculation**

The study design is targeted to achieve 80% power before October of 2017. Given our 0.048 alpha level for our final analysis, and controls anticipated to have a 13.52% readmission rate based on estimates, this requires approximately 320 patients enrolled per month (n = 2234). We assessed the feasibility of this target after observing there were approximately 508 eligible patients per month based on medical center data collected from 10/1/2015 - 9/30/2016. We noted approximately 11% of these patient would need to be

excluded after randomization due to mis-categorized hospital discharge status affecting study eligibility reducing potential monthly enrollment to 452 (n = 3164, or 1582 patients per arm). In **Table 1**, we

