**Table 1 - Power and Sample Size Scenarios** 

	Conse	rvative	Ambitious	
Control Group Readmission Rate†	13.52%	13.52%	13.52%	13.52%
Intervention Group Readmission Rate	9.60%	9.10%	10.20%	9.70%
Power	80%	90%	80%	90%
Detectable Difference	3.9%	4.4%	3.3%	3.8%
Projected Study Sample Size	1117	1117	1582	1582

\*2 group X^2 test of equal proportions (equal n's), 2-sided text, final analysis  $\alpha$  = 0.048

illustrate conservative and ambitious enrollment scenarios with estimates for 80% and 90% power. Considering we have 1 Phone Call Study Nurse and will miss enrollment days for paid time off or sick days, we opted for a more conservative power target and detectable differences of 80% and 3.9% respectively. This carries an associated enrollment of 1117 patent per arm (n = 2234, or 11 patients per day).

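### The Study Summary's 90% power for 3.5 points needs 1778 analysed patients per arm; the plan's own post-exclusion projection of 1582 gives about 85–86%, and the Power Calculation adopts a different target

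*Combined protocol and SAP*

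**What the plan says.** The Study Summary gives "Sample size: 3556 (1778 per arm"), "Target detectable difference of 3.5% (13.5% controls, 10% intervention"), 90% power by chi-square, and an accrual period of about 7 months. It states no alpha.

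The Power Calculation section describes a different design. It opens with "The study design is targeted to achieve 80% power before October of 2017" and attaches 2234 patients to that aim, at a final-analysis alpha of 0.048 and a control rate of 13.52%. It starts from about 508 eligible patients per month and expects about 11% to be excluded after randomisation for misclassified discharge status, "reducing potential monthly enrollment to 452 (n = 3164, or 1582 patients per arm"). After Table 1 it says "we opted for a more conservative power target and detectable differences of 80% and 3.9% respectively", and then "This carries an associated enrollment of 1117 patent per arm". The reason given is that there is one nurse and some enrolment days will be lost.

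Study Length and Timeline also links the halfway interim to 80% power. The Study Timeline gives "100% patient enrollment end: ~Sept 20, 2017". Statistical Analysis says "we will perform an interim analysis at 50% enrollment", and Appendix V allows a sample size adjustment after the readmission rate assumption has been checked.

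**The concern.** The headline design line and the section meant to justify it differ on N, difference and power. The headline N also appears to be a count before exclusions: 508 × 7 = 3556 exactly. The documents do not say that this is its origin, so that is an inference. If it is right, the 90% is credited to patients whom the plan itself expects to remove.

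The primary result is meant to inform a decision on enterprise-wide investment (Significance and Impact). A reader of a null result may take the chance of missing a true 3.5-point reduction to be 10%, when the plan's own projection puts it at 14–15%. The two sets of figures also leave room for different answers about what 50% enrolment means and which target an interim sample size check should use.

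**Working it through.** **Inputs.** Study Summary: 13.5% against 10.0%, 1778 per arm, 90% power. Power Calculation: alpha 0.048, control rate 13.52%, 508 eligible per month, 452 per month after exclusions, 1582 and 1117 per arm. Table 1 footnote: two-sided chi-square, equal arms. The overall alpha of 0.05 comes from Statistical Analysis.

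**Formula.** Power = Φ[(Δ − c − z·s0)/s1], where Δ = p1 − p2, s0 = √(2p̄(1 − p̄)/n), s1 = √((p1(1 − p1) + p2(1 − p2))/n), and c = 0 uncorrected or 1/n with continuity correction. For 13.5% against 10.0%, p̄ = 0.1175, 2p̄(1 − p̄) = 0.20739, and the sum of the two arm variances is 0.20678. The critical value z is 1.960 at alpha 0.05 and 1.9774 at alpha 0.048.

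**1. Reproduce the Summary.** At n = 1778, s0 = 0.01080 and s1 = 0.01078. At alpha 0.05, (0.035 − 1.960 × 0.01080)/0.01078 = 1.283, so power is 90.0%. At alpha 0.048 it is 89.7%, and with the 13.52% control rate it is 90.0%. The stated 90% therefore reproduces with the uncorrected test.

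**2. Apply the plan's own exclusions.** 452/508 = 0.89, and 452 × 7 = 3164, or 1582 per arm. At n = 1582, s0 = 0.01145 and s1 = 0.01143. At alpha 0.048 and uncorrected, (0.035 − 1.9774 × 0.01145)/0.01143 = 1.081, so power is 86.0%. With c = 1/1582 = 0.00063 the argument is 1.026 and power is about 85%.

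| Analysed per arm | Uncorrected, alpha 0.048 | Corrected, alpha 0.048 | Uncorrected, alpha 0.05 | Corrected, alpha 0.05 |
|---|---|---|---|---|
| 1778 | 0.897 | 0.887 | 0.900 | 0.891 |
| 1582 | 0.860 | 0.8475 | 0.864 | 0.852 |
| 1117 | 0.723 | 0.701 | 0.729 | 0.707 |

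Using 13.52% for controls adds less than half a point to each figure. No version reaches 90% at 1582.

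**3. Compare with Table 1.** Detectable differences from 13.52% at alpha 0.048, in percentage points:

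| Per arm, power | Uncorrected | Corrected | Printed |
|---|---|---|---|
| 1117, 80% | 3.82 | 3.90 | 3.9 |
| 1117, 90% | 4.37 | 4.45 | 4.4 |
| 1582, 80% | 3.24 | 3.30 | 3.3 |
| 1582, 90% | 3.72 | 3.78 | 3.8 |

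The corrected calculation fits the table better overall. On either version, 90% power at 1582 per arm corresponds to 3.7–3.8 points, not 3.5.

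**4. Read 3556 as the number analysed.** 3556/452 = 7.87 months from February 20, 2017, which is about mid-October 2017. The timeline ends enrolment at about September 20.

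**5. What 90% for 3.5 points would need at alpha 0.048.** 1796 analysed per arm uncorrected or 1853 corrected, so 3592 or 3706 in total. At 452 per month that is 7.9 or 8.2 months.

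**6. Candidate bases for the 50% interim.** Half of 2234 is 1117, half of 3164 is 1582, and half of 3556 is 1778.

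**7. Related counts in Sample Size Considerations.** The section gives 1117 call attempts and 334 patients reached per month. Only about 508/2 = 254 per arm per month are eligible. 1117 is the whole-study arm size, and 334/1117 is about 30%, the reach rate given under Potential Risks and Benefits. The 3048 patients over 6 months is 508 × 6, which does not match a 7-month accrual.

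**The case against.** The strongest reply is that the Summary contains no arithmetic error, and that is correct. A reader might infer a faulty formula, or see 89.7% as a shortfall. Step 1 shows otherwise: the formula is sound, and the 0.3 point comes from rounding 13.52% to 13.5%. The fault lies in the N supplied to it.

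A reader might also take 3164 as a ceiling. The documents call it potential enrolment, built from approximate historical figures. It is a projection, though the largest scenario in Table 1, and the 4–5 point gap depends on it.

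It is tempting to say that the plan never indicates which target governs. That is too strong. The Power Calculation makes an explicit choice and gives its reason, and Study Length and Timeline repeats the 80%. The Summary is the outlier. The same text suggests 2234, and so 1117, as the base for the halfway interim, although no section states that number. Nor is the test version wholly unnamed: Statistical Analysis mentions a continuity-corrected chi-square, but in a loosely worded sentence about patient characteristic groups.

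The 70–72% at 1117 per arm should not be read as the trial's expected power. It combines the Summary's difference with the conservative accrual, which the plan powers for 3.9 points.

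Intention to treat might seem to keep all 3556 in the analysis. But the Power Calculation subtracts the misclassified patients from n, Table 1 uses 1582, and Appendix V lists post-randomisation exclusions by arm.

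Finally, enrolment ends by date and there are no stopping rules, so on these documents the power line alters no test, alpha or follow-up. That limits the severity but does not remove the inconsistency.

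**Conclusion.** The point holds and should be fixed, as a matter of internal consistency; it does not threaten the validity of the trial. The Summary's 90% for 3.5 points requires about 1778 analysed per arm. The plan projects about 1582, which gives about 86% uncorrected or 85% corrected at alpha 0.048. The risk of missing a true 3.5-point reduction is then 14–15% rather than 10%. Separately, the Summary's 3556, 3.5 points and 90% conflict with the 2234, 3.9 points and 80% chosen in the Power Calculation.

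This rests on the plan's own 452 per month over 7 months, on excluded patients staying out of the primary analysis, and on the 13.5% and 10.0% event rates. Alpha 0.05 in place of 0.048, or 13.52% in place of 13.5%, does not change the conclusion.

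**What to change.** Restate the Study Summary so that it agrees with the Power Calculation, giving one analysable N, alpha 0.048, one difference, one power and one named test version. Two wordings would be consistent:

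- **The target already chosen:** 2234 analysable patients (1117 per arm), 80% power for 3.9 points, continuity-corrected chi-square, which is the version that best fits Table 1.
- **If the larger accrual is intended:** 3556 randomised, about 3164 projected analysable (1582 per arm), about 85% power (continuity-corrected) for 13.5% against 10.0%, and 90% for about 3.8 points. Study Length and Timeline, the Power Calculation and the text after Table 1 would then need revising to match.

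Name the same N as the base for the 50% interim and for Appendix V's sample size check, and say whether it counts randomised or analysable patients. Under the second wording, half could otherwise mean 1778 or 1582.

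In Sample Size Considerations, correct the monthly label on the 1117 and 334 counts, and align the 6-month period and 3048 with the 7-month accrual.

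The cost is wording and a less favourable stated power; no patients are added. Keeping 90% for 3.5 points would instead need about one more month of accrual at 452 per month.

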### Secondary Analyses:

- Subgroup Analysis of Primary Outcomes (forest plots + interaction analysis)
- Survival/Frequency Plot of Readmission events (0-45 days)
- Descriptive Demographics of Controls, Reached, Not Reached
- Heat Map of readmission rates by zip code

Figure 1 - Study Design Schematic and Enrollment Projection

#### STUDY TIMELINE: UPDATED

- 1. Adult Executive Quality Committee 3 month Update June 21, 2017
- a. Analysis: [name] (descriptive, no outcome data)
  - Table 1 Patient demographics
  - Overall VUMC readmission rate
  - Summary of phone call nurse patient interventions
- b. Presenters: [name], [name], [name]
- 2. Blinded Interim Analysis 50% patient enrollment ~July 2017
- a. Content ([name])
  - 2 week analysis window: Alpha 0.005, no stopping/futility rules
  - Patient demographics (by study arm, Table 1)
  - VUMC readmission rate by study arm and assessment of significant difference
  - Pre-specified subgroup analysis for readmission yes/no
  - Will not include the reachability index at this time.
  - Will only use death data from VUMC and available Patient Satisfaction data
  - See Appendix V for details
- b. Safety Review August 2017
  - Safety Committee Members: [name], [name], [name]
  - Review of Discharge Phone Call RN's daily reports to her supervisors for safety issues.
  - Interim Analysis Preparation and Presentation: [name]
- 3. Enrollment End 100% patient enrollment end: ~Sept 20, 2017
- a. Readmit f/u end: ~Nov 5, 2017
- b. Freeze database after Patient Satisfaction data (2mo lag) included: ~Nov 20, 2017
- c. Re-open database to add death + external hospital readmission data (6-8mo lag): ~May 20, 2018
- d. Death date source: VUMC EHR
- e. External hospital readmission data source: Vanderbilt Health Affiliated Network (VHAN)
- 4. Adult Executive Quality Committee Presentation Study End Early Findings Jan 2018
- a. Final analysis findings, except for death data
- b. 2 week analysis window: Alpha 0.048
- 5. Final Analysis June 2018
  - a. Content ([name] and [name])
    - 2 week analysis window: Alpha 0.048
    - Patient demographics (by study arm, Table 1)
    - VUMC readmission rate by study arm and assessment of significant difference
    - Pre-specified subgroup analysis for readmission yes/no
    - Identical to the Interim Analysis plan except all patient satisfaction, external hospital readmission, and mortality data will be included.

#### BACKGROUND:

Implementing a post-hospital discharge follow-up phone call program at Vanderbilt University Medical Center (VUMC) is expected to support effective patient transitions to out-patient care, improve patient satisfaction, and elevate the quality of care delivered. It will, however, add to the existing care delivery workflow and involve hiring and training additional staff. Therefore, it is crucial to rigorously quantify the impact of this program before the existing program is scaled as a larger enterprise-wide health-system intervention.

#### **OBJECTIVE**

The goal of this project is to quantify the impact of post-hospital discharge follow-up phone calls on hospital readmission within 30 days, emergency department (ED) visits, patient satisfaction, and mortality in a general medicine inpatient population. We will obtain exploratory information on patient sub-groups at high risk for readmission and those experiencing high benefit from the follow-up phone call intervention. In addition, we will obtain data on discharge plan implementation assistance needed to support a successful transition from inpatient to outpatient care amongst those reached by the intervention phone call.

### **RATIONALE**

In the current medical literature, it is unclear how follow-up calls influence these outcomes in a general medical population. Some studies have attempted to address this question, but are limited in that they target very specific patient populations, are of insufficient quality, or evaluated follow-up calls as part of a larger care bundle. We will conduct a high quality, real-time clinical care study to determine the efficacy of a follow-up phone call program.

#### STUDY DESIGN

This is a single center, pragmatic, randomized, controlled clinical trial to investigate whether a structured post-hospital discharge follow-up phone call can improve patients' transition from in-hospital to outpatient care and improve satisfaction with their care. We will also identify the discharge implementation assistance given to those in the intervention (Phone Call) group.

#### Outcome Measures

### Primary Outcome for this study is readmission within 30 days

Secondary Outcomes include evaluating: The primary outcome of readmission within 30 days within prespecified subgroups (age, gender, race, health literacy level, established primary care status, patient satisfaction, Medicare readmission penalty diagnosis status, readmission risk score), patient satisfaction between the study arms measured as mean Hospital Consumer Assessment of Healthcare Providers and Systems (HCAHPS) patient satisfaction scores, all cause VUMC ED visits, the need for assistance with discharge plan implementation, and mortality within 30 days.

#### Inclusion Criteria

The study will include VUMC patients discharged after an inpatient status hospital stay on the following General Medicine services: Riven, Morgan, Geriatrics, and Palliative Care.

#### **Exclusion Criteria**

We will exclude all patients who experience in-hospital death, leave the hospital against medical advice, are transferred to any post-acute care facility or are discharged to inpatient hospice.

#### Study Arms

VUMC Quality Committee's Post-Hospital Discharge Program is a quality initiative started in January of 2016 where a single study nurse calls as many patients after discharge as she can reach. Using a phone call intervention script and form (See *Appendix I* – Discharge Phone Call Starform) to guide the flow of each call

and screening for discharge intervention needs. After discharge, patients will be randomized to one of 2 study arms. Enrollment projections are included in *Figure 1*.

Phone Call Group (Intervention Arm): Patients will first be called with a maximum of 3 call attempts by the study nurse made up until post-discharge day 7. The semi-structured script imbedded within the Discharge Phone Call Starform is used to guide a conversation to obtain information on potential causes of hospital readmission that can be identified and addressed to improve each patient's transition to outpatient care. We will collect data on 1) outpatient care support provided to intervention group patients exposed to the phone call intervention (coordinating the receipt of durable medical equipment, facilitating a connection with home health, referral to PCP, referral to ED, requesting the assistance of case management or social work assistance for the patient, medication change initiated by the Phone Call Nurse, requesting pharmacist assistance with discharge plan details, requesting other health providers assistance, reminding the patient of planned follow up appointments, scheduling expected follow-up appointments, providing self-care education (wound care, diet, activity), providing medication dosing and administration education), 2) whether findings from the call generate a visit to emergency department or a hospital readmission. (See Appendix I's *Starform Data* section)

Usual Care Group (Control Arm): Patients assigned to the Control Group receive standard discharge planning and follow-up per the usual care of their medical providers.

#### Data Collection

Every weekday morning, a report will be generated from the Vanderbilt electronic medical record identifying all patients discharged from the hospital the previous day. This list will be transmitted securely to the study team. The list will then be randomized and uploaded to the study database within Research Electronic Data Capture (REDCap). This will occur using code written in R linked with the application program interface (API) function of REDCap. (See *Appendix II* – Randomization and REDCap API Database Upload Code). The code will upload patients assigned to the 2 study arms into separate database locations. The Intervention Arm Database includes a work list queue for the Study Phone Call Nurse. In addition, she will document interventions delivered via a form (*Appendix III* - Intervention Data Capture Form) for each patient's phone call encounter that will save this data as new variables within the database.

The Study Phone Call Nurse will continue to complete an existing form within the electronic health record, the Phone Call Starform (*Appendix I*) to document care provided via the phone call. For patients reached, the Study Phone Call Nurse will use the semi-structured script provided by the Starform to assess the patient's understanding of their discharge plan, screen for discharge assistance needs, and inquire about new symptoms requiring patient referral.

The majority of our study data will be obtained via Vanderbilt University Medical Center's Research Derivative. These variables include: 1) VUMC based primary outcome (hospital readmission to VUMC) data, 2) secondary outcome measures (patient satisfaction scores, all cause ED visits within 30 days, identified the need for assistance with discharge plan implementation, and 30 day mortality), 3) Hospital readmission risk score calculated for each patient before discharge which is included as part of the medical record, and 4) prespecified subgroup identifiers (see Figure 1).

The Research Derivative (RD) is a database of clinical and related data derived from the Medical Center's clinical systems and restructured for research. Data is repurposed from VU's enterprise data warehouse, which includes data from StarPanel, Vanderbilt Perioperative Information Management System, ORMIS (Operating Room Management Information System), EPIC, Medipac, and HEO order entry records among others. The medical record number and other person identifiers are preserved within the database. Data types include reimbursement codes, clinical notes and documentation, nursing records, medication data, laboratory data, encounter and visit data, among others. Output may include structured data points, such as ICD-9 codes or encounter dates, semi-structured data such as laboratory tests and results, or unstructured data such as physician progress reports. The database is maintained by the Office of Research Informatics under the direction of [name].

[figure not shown]
Not all patients returning to a hospital will be readmitted at Vanderbilt, and the Research Derivative data is limited to VUMC care. The inability to capture external health system readmission data is a major limitation of

readmission investigations. As a result, we have explored many methods to obtain external readmission data and found the use of the Vanderbilt Health Affiliated Network (VHAN) to be most feasible for this pragmatic study approach. We plan to overcome this obstacle, albeit in a limited way, by using the infrastructure of the Clinical Data Research Network (CDRN) to extract hospital admission and discharge data from VHAN.

Health Literacy Information will be procured from the Center for Clinical and Implementation Sciences Research Data Core.

A summary of all study variables is includes as **Appendix IV** – Study Data Summary.

Figure 2 – Flow of Discharge Phone Call Study Data Collection

